5.3 Informed Consent Procedures

Informed consent will be obtained from all providers who agree to participate at the 10 study sites at the beginning of the study. The consent process details the study procedures, including the interventions, as well as the expectations of the participating providers including participation in completion of surveys and interviews. The study team is requesting a waiver of documentation of informed consent for provider participants, as this study involves very minimal risk and would not require informed consent outside of research. The recruitment process will be conducted remotely by the central site.

The Site PI will identify eligible prostate cancer providers including urologists, PAs and NPs. Research staff members will identify email addresses through the

VA directory as needed. The Site PI will send an informational e-mail to all eligible providers to briefly explain the purpose of the study intervention and an overview of participation. Eligible providers will have the opportunity to reach out to the Site PI or research team member with any potential questions or to express preliminary interest. The email will clearly state that participation is voluntary and will not affect employment at VA.

One week following the informational e-mail, the central research team will follow-up with a recruitment email to those who have expressed interest and those who did not respond to the informational email. The team will contact each of the eligible providers by email (VA Outlook) and invite them to participate in the study through recruitment email with an information sheet attachment. The consent process will be conducted using a REDCap-based electronic consent portal. The consent portal will be developed in REDCap, a secure, web-based, HIPAA-compliant, data collection platform with a user management system allowing project owners to grant and control varying levels of access to data collection instruments and data (e.g. read only, de-identified-only data views) for other users. Potential participants will participate in the consent process by email approach from the study team, with an invitation for self-initiated access of unique link to consent portal and survey on personal portable electronic devices using web-links. Self-initiated accessing of consent portal may occur in clinic or at home; however, VA REDCap is accessible only on the VA network and login requires valid VA network ID.

Upon receipt of the recruitment e-mail, potential participants will have the opportunity to speak to a study team member to go over study procedures and ask questions. Potential participants may also opt out of future study communications upon request. The central research team and/or the Site RA will schedule either a phone call (if NY Harbor individual) or in-person (if Site RA) meeting to discuss the study procedures and to provide an opportunity for the provider to ask questions about the study and process of consent upon the request of the potential participants and to non-responders by e-mail. Contact information will also be provided (email and phone) for prospective participants to contact a member of the key study personnel with questions, prior to consent. All individuals who will have the ability to obtain informed consent have extensive human subjects' research experience. All individuals obtaining consent will be members of the research team who are designated and approved for doing so. All members of the research team have completed numerous VA research trainings as well as CITI Human Subjects Protection training. Communications including the information sheet will explicitly state that this study is purely voluntary, and there is no obligation to participate. If providers decline participation, there will be no consequences. Communications will state that this study will have no effect on employment status and their supervisor will not be aware of his/her decision to participate or not.

Participant indication of consent will be obtained using a typed signature, to be submitted through the REDCap portal. The information sheet will be included as an attachment with the recruitment email. If, when the study team speaks with potential participants, they don't remember or cannot locate the information sheet, the study members will confirm the best email address to send it to them and re-send it for reference. If a participant does consent to the study, REDCap will send an automated completion notice that will include the information sheet as an attachment. If a provider declines participation, or requests to no longer be contacted regarding this study, the study team will not contact that individual again. Follow-up emails will be sent one week after initial contact to those who do not respond. Up to 3 follow-up emails will be sent to non-responders. The central research team will make phone calls to the numbers listed in the VA directory in attempt to reach individuals who did not respond to emails. The research team will end follow-up after 2 unsuccessful phone calls to non-responders.

The research team will re-send the REDCap consent portal after the intervention has begun if a non-participating provider requests to be included in the study during or following the study kickoff site visit. The research team may send one follow-up email or follow-up phone call as necessary, and all recruitment efforts for providers at the given site will cease at that time.

Study team members will record and receive verbal consent to audio record from participants for interviews that occur over the phone through Micrososft Teams. Participants in the qualitative portion of the study will have already consented by agreeing to participate in the study during the recruitment process.

Informed consent will not be required of patients due to a waiver of HIPAA authorization and a waiver of informed consent. There will be no active participation of patients in this study; the study team will access patient electronic health records in order to monitor trends in imaging among prostate cancer patients.

5.4 Inclusion/Exclusion Criteria

Provider Criteria

- Inclusion criteria
 - Urology Chiefs and attending urologists employed through the VA (full-time, part-time, WOC) at one of the 10 participating sites; Physician Assistants and Nurse Practitioners employed through the VA at one of the 10 participating sites that work in the respective urology clinics
 - o Providers may be any gender or race/ethnicity
 - Qualitative portion only: Urology Chiefs and/or frontline staff physicians; participating PAs & NPs having cared for at least 5 men with incident prostate cancer within the previous 6 months

Exclusion criteria

Urology Residents

In efforts to avoid potential coercion, Urology Residents are excluded from the study due to the hierarchical culture of surgical training program in addition to preliminary findings that imply that they strictly adhere to attending preference.²⁹

Patient Criteria

Patients will not be directly recruited into the study. We will obtain a waiver of HIPAA authorization and informed consent to analyze electronic health records of patients at the 10 participating sites.

5.5 Study Evaluations

Screening

Physicians and other eligible providers will be identified based on their employment in the Urology sections at the 10 participating sites. Urology Chiefs and local site-PIs have already been identified.

Questionnaires

Prior to the initiation of the intervention, immediately following the e-consent process, all provider participants will be asked to complete a demographic questionnaire as well as validated survey measures. The demographic questionnaire will ask providers questions about age, race/ethnicity, and details about their time as urologists/providers, such as years in practice and training focus. Full, Part-time, or WOC VA status of the providers will be determined administratively. After the demographic questionnaire the participants will complete the ORCA scale, 24 and the EBPAS scale. 25 When the intervention is complete three additional measures will be administered to participants: Adoption of Information Technology Innovation-Compatibility Subscale, 27 Level of Success Instrument, 28 and a Self-Assessment of Contextual Fit. 26 Participants will also complete the ORCA scale again as a pre/post measure. The research staff will prepare the VA-approved REDCap portal for virtual distribution and collection of results. The staff will provide access information via VA Outlook to distribute the survey instruments electronically, including unique links to unique portals to collect data from each participant. REDCap is a secure, VA-approved web application that facilitates the collection and entry of research data. The main research staff at NY Harbor will be able to access the questionnaire results directly through the secure REDCap project account. The main research staff will have exclusive access to this account. As per VHA Record Control Schedule 10-1 8300.6, collection of records will be cutoff at the end of the fiscal year after completion of the research project, and results will be destroyed 6 years after cutoff. All responses collected will be deidentified. Results will be reported as aggregate. Individual responses will not be shared with the Urology Chiefs, and the Urology Chiefs will not be aware of who has completed the survey or not.

Qualitative Interviews

Qualitative interviews will be conducted using an interview guide developed using CFIR. The aim of the interviews is to understand the acceptability and sustainability of the intervention. There is a section on the interview guide that is specifically for the Urology Chiefs and Site PIs, as leaders of this project. These questions explore the institutional perspectives of intervention implementation and attitudes towards sustainability of the intervention. An investigator along with a member of the main research staff will travel to each of the participating sites to conduct the interview in-person, or the interviews will be held over the phone by a member of the central investigative team (investigator or staff member). Data from the interview will be collected through the VA Microsoft Teams application and uploaded to a secure internal research drive for transcription.

Additionally, the central research team will collect ongoing qualitative data from site research team members about the implementation of the intervention every 6 months post commencement via informal phone interviews. Demographic information of LSIs and Local Rcs will be recorded.

All evaluation materials are included as a separate attachment with the protocol.

5.6 Data Analysis

All data will be managed at VANYHHS by the Data Manager, Research Coordinator, and Project Manager. They will collect, clean, and analyze datasets. Other members of the main study team will analyze aggregated or de-identified data. Statistical analyses will be performed using the SAS 9.1.3 Service Pack 4 statistical package (SAS Institute, Cary, NC) and Excel 2010 (Microsoft Corporation, Seattle, WA). Qualitative data will be analyzed using NVivo 10 (QSR International). REDCap is a secure, VA-approved web application that facilitates the collection and entry of research data. A private, password protected REDCap project will be created for this study. Study team members will ascertain the input data from the questionnaire as well administered to participants. REDCap not only stores data but can generate descriptive statistics. Site-specific results will be deidentified and will not be shared with anyone beyond the central research team. Specifically, only aggregated data will be shared with Chief or Site PI. Site-specific information will be collected for analysis purposes only; results will be reported as aggregate.

Quantitative Analysis

Quantitative data for this study is from VHA's Corporate Data Warehouse (CDW). VINCI, VHA's secure data environment will be used to identify prostate cancer patients in CDW as well as their imaging tests, demographic information, and clinical history. The VINCI team will extract required data from CDW tables and create a work environment for our team on secure VINCI servers in Salt Lake City. VSSC's Cancer Care Cube (CCC) will be used to generate timely data for Audit and Feedback. CCC permits rapid access to

accurate nationwide VA cancer registry data³⁰ from the clinical OncoTrax system, uploaded once monthly. To address potential reporting delays, we will check the validity of the Oncotrax data by comparing them with CAPRI data biweekly - a focused review of about 200 charts a week. In further efforts to avoid delays due to lags in CDW data availability, the local IT specialist will run a reoccurring monthly report in CPRS in attempt to identify patients diagnosed with prostate cancer in real-time. The results will yield patient name, SSN, and presumed date of prostate cancer diagnosis. The IT specialist will send the results of these queries to the central research team via PKIencrypted email on VA outlook periodically. If the IT specialist at a site is unavailable to produce these reports, another member of the Local Clinical Advisory Committee will send either a list of newly diagnosed prostate cancer patients or a list of patients receiving prostate biopsies at that site via PKI-encrypted email to the central research team. The central research team will verify and validate this data using concentrated chart review within CAPRI. Due to local practice differences at the Madison VA only, the central research team is unable to verify receipt of imaging in CAPRI, such as bone scan or CT, (our primary outcome) without access to the local consult notes in CPRS. Therefore, the central research team will verify eligibility status of patients sent from the initial local CAC data pull. The central research team will send this confirmed list back to the local research coordinator via PKI-encrypted email for verification of imaging receipt and date of imaging. The local research coordinator will ascertain the imaging order and status via local consult notes in local CPRS system. The local research coordinator will then send the confirmation of imaging completed, type of imaging, and date received via PKI-encrypted email to the central research team. This will serve as a supplemental source of data to improve data validity, accuracy, and quality for both feedback reports and overall imaging rates. The study team will collect the following data from CAPRI: date of birth, zip code, marital status, race/ethnicity, Gleason score, date of diagnosis, PSA, clinical stage, date of medical appointments, diagnostic procedures/treatment, imaging ordered, and treating provider. This will guarantee the fidelity of the data used for Audit and Feedback and provide insight into the timing with which data from each individual site are updated for future projects. CCC data will be stored securely in VINCI where it will be linked to CDW when necessary. We will request remote CAPRI access to all 10 study sites for the central research data team from the National Information Security Officer (ISO) following Central IRB approval.

The sample size of 10 study sites was determined to ensure appropriate power for our primary outcome: differences in the rate of inappropriate prostate cancer imaging. For the sample size calculation of a stepped wedge trial, the key variables are the number of clusters (i.e., sites), I; the number of distinct time points or intervals being compared, T; and the number of outcome observations per time point, N (i.e., the number of individual patients with the outcome per cluster, per time interval).⁴ We assume the model, $Y_{ij} = \mu + \alpha_i + \beta_j + X_{ij}\theta + e_{ij}$, where α_i is a random effect for cluster i such that $\alpha_i \sim N(0, \tau^2)$, β_j is a fixed effect corresponding to time interval j, X_{ij} is an indicator of whether the intervention has been implemented in cluster i at time j (1=intervention; 0=control), θ is treatment effect and $e_{ij} = \sum_k e_{ijk}/N$ are independent and identically distributed $N(0, \sigma^2)$

and $\sigma^2 = \sigma^2_e/N$. Let Y_{ij} be the mean for cluster i at time j. Assume testing the hypothesis H_0 : $\theta = 0$ versus H_A : $\theta = \theta_A$, where θ_A is the treatment effect size. The approximate power for conducting a 2-tailed test of size alpha is power =

$$\Phi\left(\left(\theta_A/\sqrt{Var(\hat{\theta})}\right)-Z_{1-\alpha/2}\right)$$
 where Φ is the cumulative standard normal distribution

function, $Z_{1-\alpha/2}$ is the $(1-\alpha/2)th$ quantile of the standard normal distribution function and $\hat{\theta}$ is the estimated effect size. The estimated number of patients exposed to the intervention will be 750, compared to 750 control patients, which will provide sufficient power for even modest improvements in imaging rates among low-risk men. Assuming 10 time periods (Q2-Q11), an estimate for baseline imaging among men with low-risk prostate cancer of 40% in the usual care group, and a decrease to 20% guideline-discordant imaging (absolute difference of -0.20), 10 clusters (sites), 15 patients with low-risk prostate cancer per quarter x 10 study sites x 10 quarters is estimated to impact 1500 total patients out of 6000 patient charts reviewed (a conservative estimate based on analysis of VINCI data), an alpha of 0.05, and a coefficient of variation of 0.40, accounting for clustering, we would estimate having a power of >0.999. This is a conservative estimate in terms of the expected effect of the intervention on prostate cancer imaging rates and assumes a high coefficient of variance with outcomes highly correlated with site. A more conservative post-intervention rate of imaging of 28.7% would reduce power to 0.80.

Similarly, we estimate that we will have sufficient power to detect increases in appropriate imaging among men with high-risk prostate cancer. Assuming 10 time periods (Q2-Q11), an estimate for baseline appropriate imaging of 66% in the usual care group, and an increase to 86% (for an absolute difference of +0.20), 10 clusters (sites), 5 at patients with high-risk prostate cancer per quarter (a conservative estimate based on analysis of VINCI data), alpha of 0.05, a coefficient of variation of 0.40, we estimate power of 0.89.

We will also perform exploratory, individual-level analyses. If providers consent to participate in the study, then these imaging outcomes will be linked to their survey and qualitative data. For non-participants, imaging patterns alone (with no additional data) will be analyzed in a de-identified manner.

Qualitative Analysis

Qualitative data will add depth and detail, complementing the other findings to explain and illustrate quantitative results. In-depth interviews at the conclusion of the study will explore providers' experiences with the intervention and explain the important implementation-related domains from CFIR.²² The exploratory nature of this component will permit the identification of new ideas and inform the generation of inductive hypotheses regarding factors motivating guideline-concordant imaging. We will also ask a short series of questions exclusively to all Urology Chiefs and Site Pls (N=20) to explore institutional and managerial perspectives of implementation and attitudes towards sustainability of the intervention.³¹ Data gathered will be critical to the plan to

disseminate the intervention to other VAMCs nationally. We anticipate recruiting a subset of approximately 20-30 frontline providers across the 10 participating study sites in order to reach theoretical saturation. There are 79 practicing urologists at all 10 sites (10 Chiefs and 67 frontline practitioners) so we anticipate no difficulties in reaching our recruitment goal. Qualitative results will be analyzed using NVivo software (QSR International). NVivo will allow for the organization, coding, and analysis of interview transcripts. Results obtained from these triangulated quantitative and qualitative components will be integrated, 32,33 a key procedure in mixed methods analysis. Demographic information will be collected from participants to aid in the analyses.

Cost Analysis

Clinical care cost data will be accessed primarily through the Health Economics Resource Center (HERC) Average Cost File. HERC has created estimates of the cost of all VA health care encounters that have taken place since October 1, 1998. These data are accessible approximately 6-8 months following end of the fiscal year. These data will allow for comparable standardized prices to be applied across all VHA facilities for all follow-up care activities. Cost data will also be obtained from billable private insurance claims. VHA's Medical Care Recovery Program attempts to collect for care performed at VHA when a VA user has private insurance. We will identify subjects in our cohort who have billable private insurance and flag these subjects for exclusion in sensitivity analyses as they may be likely to be more reliant on community care than VA-users without private billable insurance. Preliminary analysis in VISN20 identified that out of a cohort of 260,743 subjects, 17,141 (6.6%) had billable insurance. This variable is available in the CDW.

We will also estimate the cost of implementing the intervention using methods described by Liu et al. in their paper documenting organizational costs for implementing a depression care quality improvement intervention into VHA primary care practices.³⁴ These methods allow for the documentation of organizational costs associated with the implementation effort itself, not just the costs associated with changes in patient care, whose calculation we describe above. We will collect data on participant hours and intervention related activities directly related to the implementation effort. Implementation costs are related to travel, clinical informatics, training sessions, conference calls, development of training materials, email communication, and any other activities spent counseling, training, or supporting personnel at the study sites. Participants will include any individual (provider, study staff, administrator) participating in the implementation project. Data sources used for estimating costs will include interviews, surveys, e-mail communications, project schedules, meeting minutes, project cost records, and government salary information. Costs will be estimated based on length of interviews and surveys, email word count, time of telephone calls, and government travel budgets based on calculated reference ranges for such expenses, as described by Liu et al. 34

Outcomes

The study's Primary Outcomes determined from the above data sources will be:

Specific Aim 1

- Facility-level utilization of bone scan or abdominal/pelvic CT or abdominal/pelvic MRI among men with newly diagnosed, low-risk prostate cancer. (Inappropriate Imaging)
- Facility-level utilization of bone scan or abdominal/pelvic CT or abdominal/pelvic MRI among men with newly diagnosed, high-risk prostate cancer. (Appropriate Imaging)

Specific Aim 2

- Provider-level utilization of bone scan or abdominal/pelvic CT or abdominal/pelvic MRI among men with newly diagnosed, low-risk prostate cancer. (Inappropriate Imaging)
- Provider-level utilization of bone scan or abdominal/pelvic CT or abdominal/pelvic MRI among men with newly diagnosed, high-risk prostate cancer. (Appropriate Imaging)
- 3. Provider attitudes regarding prostate cancer imaging guidelines and the behavioral intervention

Specific Aim 3

1. Net cost of implementation of physician behavioral intervention VHA. This file will be used to quantify facility-level workforce and imaging technology.

Facility-level descriptors will be obtained from the 2009 VHA Oncology Services Survey.³⁵ As part of the Office of Patient Care Services initiative to conduct systematic program reviews, Oncology Services conducted a survey of cancer care services in VHA.

Missing Data

Missing data has the potential to affect the validity of our results. We foresee 4 potential sources for missing data and propose strategies to deal with them.

- Improper transcription into Oncotrax and CCC: to overcome this, we will train our centrally-located, full-time Research Coordinator to identify missing data fields and search for this information in CAPRI. We expect the study to follow 60 patients from 10 sites per quarter, or a manageable 12 patients per business day.
- 2. Patients seeking care in the private sector through the Veterans Choice Act: Fortunately, when the VA pays for imaging tests, they are indicated in CAPRI. Outside healthcare providers have to send back the statement to collect payment so this information will be manageable to track.³⁶
- 3. Patients seeking care in the private sector through Medicare: [name] found 67% of veterans with an elevated PSA followed up within VHA in the subsequent 24 months.^{37,38} We assume that follow-up will be improved among men with a

- cancer diagnosis already having chosen to undergo prostate biopsy within VHA. At the completion of the study, we will request CMS records using VIReC's CMS-VA linkage to identify any missing studies performed by a Medicare provider.³⁹
- 4. Patients seeking care in the private sector through private insurance: there is no reliable way to ensure completeness of these data. We will review CAPRI notes for documentation of outside care but may not be able to confirm that none took place. This phenomenon should occur with equal frequency in the control and the intervention sites and should bias our results to the null.

In spite of our best efforts, it is likely that some data will remain missing. The full information maximum likelihood (FIML) method will be used to handle missing data as a less stringent assumption of missing-at-random will be made. Simulation studies have shown that no other missing data handling method performs better than the FIML regardless of the mechanism by which the missing data are generated. 40,41

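### The only Aim 1 model in the plan has no patient covariates, although age, PSA and Gleason score are to be collected, so some precision is probably forgone.

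*Combined protocol and SAP*

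**What the plan says.** The model is in section 5.6 (Quantitative Analysis), in the paragraph that begins "For the sample size calculation of a stepped wedge trial, the key variables are the number of clusters". For the mean of each site in each interval it has an overall mean, a normally distributed random site effect, a period term that "is a fixed effect corresponding to time interval j", a 0/1 intervention indicator and independent error. Nothing in it describes the patients.

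No separate Aim 1 analysis model is stated. The same section promises exploratory individual-level analyses without naming covariates, and the Outcomes text mentions facility-level descriptors without saying how they would enter a model.

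Patient data are nonetheless planned. The chart-review list in section 5.6 includes date of birth and "Gleason score, date of diagnosis, PSA, clinical stage, date of medical appointments, diagnostic procedures/treatment, imaging ordered, and treating provider". The purpose given there is data quality for the feedback reports and the imaging rates, not adjustment.

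Two places bear on completeness. The patient exclusion in section 5.2 for absent PSA, stage or Gleason data can be read as removing men who lack any one item, or only men who lack all three. The Missing Data text in section 5.6 expects some data to stay missing and plans full information maximum likelihood under missing-at-random.

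**The concern.** Each quarter contributes newly diagnosed men, so the make-up of a site's cell varies from quarter to quarter. Where age, PSA or Gleason score predicts whether a man is imaged, a model without them leaves that variation in the error term. The standard error is then larger than it need be. The low-risk scenario of 40% to 28.7% is planned at a power of only 0.80, and the high-risk cells are small, so a modest gain from data already being gathered is worth having.

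Leaving the covariates open has a second cost. The central team reviews imaging outcomes throughout the study and issues quarterly feedback, so a list chosen late could be chosen with outcomes in view.

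A third, weaker reason is protection against a systematic change in a site's case mix that coincides with its go-live. Period effects cannot remove that.

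**Working it through.** **Inputs from section 5.6**
- Test: "conducting a 2-tailed test of size alpha", with "an alpha of 0.05, and a coefficient of variation of 0.40".
- Low-risk control rate: "an estimate for baseline imaging among men with low-risk prostate cancer of 40% in the usual care group".
- Low-risk intervention rate and sites: "a decrease to 20% guideline-discordant imaging (absolute difference of -0.20), 10 clusters (sites"; the more cautious scenario is 28.7%.
- Low-risk cell size: "15 patients with low-risk prostate cancer per quarter x 10 study sites x 10 quarters".
- High-risk: 66% to 86%, 5 men per quarter, read here as per site.

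**Inferred layout.** Section 5.1 has an all-control baseline, and section 5.6 counts 10 periods labelled Q2-Q11. I take T = 11 periods (baseline plus 10 steps), I = 10 sites, one site crossing per step.

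**Step 1: reproduce the stated powers.** The Hussey-Hughes variance is

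Var(θ̂) = Iσ²(σ² + Tτ²) / [(IU − W)σ² + (U² + ITU − TW − IV)τ²]

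with σ² = p̄(1 − p̄)/N, p̄ the mean of the two rates, and τ = 0.40 × control rate. The layout gives U = 55 and W = V = 385, so IU − W = 165 and U² + ITU − TW − IV = 3025 + 6050 − 4235 − 3850 = 990.

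Low-risk, 40% to 28.7%:
- p̄ = 0.3435; σ² = 0.2255/15 = 0.01503; τ² = 0.16² = 0.0256.
- Var = 10 × 0.01503 × (0.01503 + 0.2816) / (165 × 0.01503 + 990 × 0.0256) = 0.04460/27.82 = 0.001603; SE = 0.0400.
- Power = Φ(0.113/0.0400 − 1.96) = 0.806 (stated 0.80).

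High-risk, 66% to 86%:
- p̄ = 0.76; σ² = 0.1824/5 = 0.03648; τ² = 0.264² = 0.0697.
- Var = 0.2930/75.02 = 0.003906; SE = 0.0625.
- Power = Φ(0.20/0.0625 − 1.96) = 0.893 (stated 0.89).

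Low-risk, 40% to 20%, gives 0.9993 (stated >0.999). With T = 10 and no baseline the three low-to-high-risk figures, in the order 40% to 20%, 40% to 28.7% and high-risk, are 0.999, 0.776 and 0.869. T = 11 therefore fits the plan better.

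**Step 2: effect of adjustment.** Multiply σ² by (1 − R²), where R² is the share of within-cell variance explained. R² is assumed.

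| R² | Low-risk SE | Low-risk power (28.7%) | High-risk SE | High-risk power |
|---|---|---|---|---|
| 0 | 0.0400 | 0.806 | 0.0625 | 0.893 |
| 0.02 | 0.0396 | 0.813 | 0.0619 | 0.898 |
| 0.05 | 0.0391 | 0.825 | 0.0610 | 0.907 |
| 0.10 | 0.0381 | 0.844 | 0.0594 | 0.920 |

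For scale, a binary covariate with prevalence π and a 20-point difference in imaging has R² = π(1 − π) × 0.20² / (0.40 × 0.60). That is 0.035 at π = 0.3 and 0.042 at π = 0.5.

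**Step 3: can case mix bias the estimate?** Assume a subgroup imaged 20 points more often grows by 10 points, which moves a site mean by 0.10 × 0.20 = 2 points. Through the same generalised least squares fit (low-risk inputs):
- The same drift at all sites: bias 0, absorbed by the period effects.
- A shift at one site, aligned with its own step: 0.1-0.3 points.
- Shifts at random times and in random directions at every site: mean about 0, SD 0.4 points, against an SE of 4.0 points.
- A shift aligned with the step at every site: the full 2.0 points.

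A larger high-risk example: a 20-point mix change with a 20-point imaging difference moves one site's rate by 4 points. Aligned exactly with that site's go-live, it moves θ̂ by 0.17-0.53 points, depending on the step, against an SE of 6.25 points.

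**The case against.** The strongest objection is that this is a power model. Power formulas usually omit covariates, and nothing says Aim 1 will be analysed with these terms alone. That is right, and a reader should not infer that the plan commits to an unadjusted analysis. But no other Aim 1 model is given. Whether the analysis is unadjusted or simply left open, the remedy is the same.

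The gain may also be small. R² has no source in the documents. The Order Check text in section 5.1 suggests that PSA, Gleason score and stage help define the risk groups, so they would vary less within a group. This stands and points to the low end of the range.

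A reader might infer that case-mix shifts will pass for an intervention effect. The documents do not support that as an expectation. Chance variation in who is diagnosed is already part of p̄(1 − p̄)/N and widens the interval; counting it again as bias would be double counting. Stable site differences go largely to the site effect, common drift goes to the period effects, and go-live time is randomised. Only systematic site-by-time shifts aligned with go-live would bias the estimate, and the documents give no evidence of them. Section 5.6 does allow case-finding sources to differ between sites, so such shifts are possible.

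A reader might also infer that these fields will be available for every man. The ambiguous exclusion and the expected residual missingness do not support that.

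Finally, recorded clinical stage may itself reflect imaging. Adjusting for such a value would condition on something the outcome affects. This stands and limits the covariate list.

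**Conclusion.** The point holds as a low-cost improvement in efficiency and prespecification, not as an error in the power calculation: all three stated powers reproduce. At an assumed R² of 2-10%, adjustment cuts the SE by about 1-5%. It adds roughly 1-4 points of power in the low-risk 28.7% scenario and 1-3 points in the high-risk group, probably nearer the lower figures. In the 40% to 20% scenario it makes no practical difference. Protection against bias is a secondary reason. The figures rest on the assumed R², the inferred 11-period layout, 5 high-risk men per site per quarter, and the normal approximation that the plan itself uses. The change is advisable but not essential to the validity of the trial.

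**What to change.** In section 5.6, state the Aim 1 analysis as a patient-level mixed model, fitted separately for low-risk and high-risk men, with:
- a random site effect, fixed quarter effects and the intervention indicator;
- age at diagnosis, log PSA and biopsy Gleason score as fixed covariates, with the list locked before the Aim 1 model is fitted;
- clinical stage only if the recorded value was fixed before staging imaging.

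Say how missing covariate values are handled and how this fits with the planned likelihood-based approach. Clarify the section 5.2 exclusion, since it decides how much covariate data can be missing. Report the standardised risk difference, which keeps the effect on the scale used for the sample size, with the unadjusted estimate alongside.

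The cost is some added wording, a little more analysis work and the handling of some missing covariate values. The covariates are already on the collection list. With about 5 high-risk men per site-quarter the list should stay short, because each added term has an estimation cost.
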